6.6 Restrictions

6.6.1 Prior Therapy

Prior therapy excluded for this study consists of the following:

- Psychotropic or other medications, which in the Investigator's opinion would be likely to substantially confound test results, and the dose and regimen of which cannot be kept constant throughout the study.
- The patient cannot sustain absence from aspirin, non-steroidal medications, or medications that affect blood clotting within 1 week prior to a relevant study related procedure (eg, device implantation if applicable) or medications within 1 week before any procedures in which any change in clotting activity would be deleterious.
- The patient has received any investigational drug or device intended as a treatment for MPS IIIA within the 30 days prior to the study other than rhHNS or is enrolled in another study that involves an investigational drug or device.
- Hematopoietic stem cell or bone marrow transplant.

6.6.2 Fluid and Food Intake

Food and fluid intake are not restricted over the course of the study, with the exception of hospital standard pre-anesthesia dietary restrictions.

6.6.3 Patient Activity Restrictions

There are no restrictions on patient activity in this study.

6.7 Treatment Compliance

rhHNS is administered under controlled conditions by the Investigator; therefore, full patient compliance with study treatment is anticipated in this study.

6.8 Packaging and Labeling

Drug product will be supplied in a 3 mL clear, colorless glass (Type 1) vial. Each vial holds an extractable volume of 1 mL of rhHNS. The closure is a gray, 13 mm stopper composed of butyl rubber with a fluoro resin lamination. The overseal is an aluminum seal with a flip-off, plastic, tamper evident cap.

See the Pharmacy Manual for additional details.

6.9 Storage and Accountability

Drug product should be stored refrigerated (2 to 8°C); drug product may not be stored beyond the expiration date on the vial.

6.10 Investigational Product Retention at Study Site

All rhHNS study drug delivered to an Investigator will be recorded and accounted for throughout the study. All rhHNS study drug must be recorded on a patient-by-patient basis. The lot number of the IDDD and the date and time of administration of the study medication will be documented on the appropriate eCRF.

All unused study medication and other study materials are to be returned to the Sponsor or its designee or disposed of after Sponsor approval per site policy after study completion.

7 STUDY PROCEDURES

7.1 Informed Consent

Study procedures will be conducted only after written informed consent for the patient to participate in this study is provided by the parent(s) or the patient's legally authorized representative(s) and assent from the patient (if applicable). Detailed descriptions of patient evaluations required for this protocol are described in this section. These evaluations will be performed during the indicated days and weeks of each study month (see [Appendix 1](#) Schedule of Events).

All data collected are to be recorded on the appropriate eCRF. Blood, urine and CSF volumes to be collected for each clinical laboratory measurement are described in detail in the Laboratory and/or Study Operations Manual.

7.2 Physical Examination

A physical examination of each patient will be performed as detailed in [Appendix 1](#) Schedule of Events.

Note: if the patient's hearing cannot be assessed during the physical examination, the patient will have an Ears, Nose, and Throat Evaluation performed under anesthesia at the screening/start of study visit. If it is determined that the patient requires pressure-equalization (PE) tubes, they may be implanted during that evaluation (see Section 7.10). Note: PE tubes may be re-implanted if they fall out during this study.

The physical examination findings will be recorded on the eCRF and will include a review of the patient's general appearance as well as the following evaluations:

- Head and neck
- Eyes, ears, nose, and throat
- Chest and lungs
- Cardiovascular
- Abdomen
- Skin
- Lymphatic
- Musculoskeletal
- Neurological
- Endocrine
- Genitourinary

7.3 Height and Weight

Height or length (cm), and weight (kg) will be measured once and recorded on the eCRF.

7.4 Head Circumference

Head circumference (cm) will be measured and recorded on the eCRF.

7.5 Vital Signs

Vital signs (blood pressure, heart rate, respiratory rate, and temperature measurements) will be measured and recorded on the eCRF.

7.6 Electrocardiography

7.6.1 Electrocardiograms

An ECG will be performed. Each ECG will include an assessment of heart rate, sinus rhythm, atrial or ventricular hypertrophy, PR, QRS, QT, and QTc intervals. The ECGs will be conducted in accordance with the clinical site's standard practice(s), and will be read locally at the clinical site. Identification of any clinically significant findings and/or conduction abnormalities will be recorded on the eCRF.

7.7 Clinical Laboratory Tests

Blood, urine, and CSF samples will be collected as described below for clinical laboratory testing. Procedures for collection and handling of samples are included in the Laboratory and/or Study Operations Manual.

Patients will be in a seated or supine position during blood collection. Clinical laboratory tests will include hematology, serum chemistry, and urinalysis.

Laboratory Parameters

Clinical laboratory tests will be performed at a central laboratory. Clinical laboratory tests will include the following:

7.7.1 Hematology

-
- | | |
|--|--|
| • Hematocrit (Hct) | • Mean corpuscular volume (MCV) |
| • Hemoglobin (Hgb) | • Platelet count |
| • Mean corpuscular hemoglobin (MCH) | • Red blood cell (RBC) count |
| • Mean corpuscular hemoglobin concentration (MCHC) | • White blood cell (WBC) count with differential |
-

7.7.2 Serum Chemistry

-
- | | |
|--|---|
| • Albumin (ALB) | • Glucose |
| • Alkaline phosphatase (ALK-P) | • Lactate dehydrogenase (LDH) |
| • Alanine aminotransferase (ALT; SGPT) | • Phosphorus |
| • Aspartate aminotransferase (AST; SGOT) | • Potassium (K) |
| • Blood urea nitrogen (BUN) | • Sodium (Na) |
| • Calcium (Ca) | • Total bilirubin |
| • Carbon dioxide (CO ₂) | • Direct bilirubin |
| • Chloride (Cl) | • Total cholesterol |
| • Creatinine | • Total protein |
| • Creatine kinase (CK) and subtypes | • Triglycerides |
| • Gamma-glutamyl transferase (GGT) | • Uric acid |
| • Globulin | • Human Chorionic Gonadotropin (βhCG)
Pregnancy Test |
-

In addition a leukocyte pellet will be prepared, stored frozen, and will be used for additional disease-related laboratory studies, including possible assessment of cross-reactive immunologic material (CRIM).

7.7.3 Pregnancy Test

A pregnancy test will be performed on Day 1 of each dosing week. Pregnancy testing will be performed using either a serum or urine sample (at the discretion of the site), and only on females who have reached menarche. All pregnancy testing and the reporting of results will be performed locally by the clinical site staff. Study drug must not be administered in the event of a positive or inconclusive pregnancy result.

7.8 Urinalysis

Patient catheterization may be required for obtaining urine samples (if deemed necessary by the Investigator).

7.8.1.1 Standard Urinalysis

The following urinalysis parameters will be performed at a central laboratory: pH, macroscopic and microscopic evaluations.

7.8.1.2 Urine Heparan Sulfate and Heparan Sulfate Derivatives

A urine sample will be collected for the determination of heparan sulfate and heparan sulfate derivatives and the analysis will be performed at Shire HGT or designated laboratories. A urine sample from each visit will be reserved for possible exploratory biomarker studies that may provide new indicators or markers of MPS IIIA disease severity or progression.

7.8.2 Cerebrospinal Fluid Assessments

Cerebrospinal fluid sample collection, processing, and shipping instructions will be provided in the Laboratory and/or Study Operations Manual. A CSF sample will be reserved for possible exploratory biomarker studies for MPS IIIA disease.

Each CSF sample collected will be assessed for appearance and will be analyzed using the assays listed in Sections 7.8.2.1, 7.8.2.2, and 7.8.2.4. In addition, as more is learned about Sanfilippo CNS pathology and etiology, future exploratory assays of CSF metabolites, protein or RNA may become used as they become available in the future.

7.8.2.1 Cerebrospinal Fluid Cell Counts

An aliquot of each CSF sample collected will be evaluated for CSF standard chemistries, glucose, protein, and cell counts. These assessments will be performed at the local laboratory.

7.8.2.2 Cerebrospinal Fluid Heparan Sulfate Levels and Heparan Sulfate Derivatives

An aliquot of each CSF sample collected will be quick frozen as per the Laboratory and/or Study Operations Manual for subsequent determination of CSF heparan sulfate and heparan sulfate derivatives at Shire HGT laboratories.

7.8.2.3 Anti-rhHNS Antibodies

An aliquot of each CSF sample collected will be quick frozen as per the Laboratory and/or Study Operations Manual for subsequent determination of anti-rhHNS antibodies at Shire HGT or Shire HGT designated laboratories.

7.8.2.4 Cerebrospinal Fluid Biomarkers

An aliquot of each CSF sample collected will be quick frozen as per the Laboratory and/or Study Operations Manual for subsequent determination of MPS exploratory biomarkers at Shire HGT laboratories.

7.8.3 Sample Collection, Storage, and Shipping

Sample collection, processing, and shipping instructions will be provided in the Laboratory and/or Study Operations Manual to be provided by Shire HGT.

CSF, urine, and serum samples may be reserved for potential, future, biomarker studies. Samples will be stored securely to ensure patient confidentiality.

7.9 Anesthesia

Administration of anesthesia/sedation will be given prior to obtaining CSF (when the use of the IDDD is precluded), prior to performing a MRI of the head, the ABR, the CSF opening pressure, and the partial revision or replacement of the IDDD (if applicable).

See [Appendix 1](#) for the Schedule of Events. When logistically feasible, the MRI, ABR, and surgical implantation of the IDDD may be performed together to reduce exposure to general anesthesia.

Note: The neurologic exam and the neurocognitive and developmental assessments must be performed prior to the administration of anesthesia.

7.10 Audiometry and Auditory Brainstem Response

The rare attenuated patients with MPS IIIA with high levels of cognitive functioning will have hearing tests via clinical audiometry measurement performed using age-appropriate testing methods based on the child's developmental age at the time of the testing. It is anticipated that most of the cognitively-impaired and/or behaviorally-deteriorated patients with Sanfilippo A will be unable to cooperate with a (conscious) hearing evaluation. In these instances, the Investigator will utilize his best clinical judgment to estimate the extent of hearing loss (if any) during the physical examination. In this situation, a specific evaluation of hearing loss will occur during an examination of waveforms in the ABR (see below). If the patient has a history of multiple instances of otitis media or evidence of clinically-significant otitis media on physical examination, which the Investigator believes causes significant conductive hearing loss and impairment of daily living, the Investigator will discuss and offer the parent or legally authorized representative(s) placement of PE tubes as part of the scheduled anesthesia. A patient's PE tubes may be replaced if they fall out during the course of this study.

The ABR will be conducted under anesthesia. The ABR findings will be considered within normal limits if, after applying appropriate correction factors, the waveforms reveal normal morphology.

7.11 Magnetic Resonance Imaging of the Head

The regional brain volume will be assessed through a MRI, of the head. The patient will be under general anesthesia for this assessment. All MRIs will be centrally read by the University of Minnesota Medical Center. Refer to the Study Operations Manual for specific procedures and precautions.

7.12 Surgical Re-implantation of the IDDD

If a patient's IDDD becomes nonfunctional or infected, it will be replaced or revised so that the patient can remain on study. Management details are provided in [Appendix 3](#). Procedures for implantation are detailed in the device's Instructions for Use Manual and in the training materials provided by Shire HGT. The patient will be under general anesthesia for this procedure. The CSF opening pressure will be recorded when the intrathecal space is first entered at the time of the IDDD re-implantation. Standard hospital procedure for surgery will be followed and will include an X-ray to confirm that the device has been (1) surgically implanted correctly (correct orientation of the locking device on the access port), and (2) positioned so that the intrathecal catheter tip is at the mid-thoracic level (a check list is provided in the Study Operations Manual).

A post-operative check of the IDDD and incision will be performed on Day 4 following surgery. X-rays may be performed to check placement of the device, as needed, throughout the study (see Section 7.12.1 for limits on the number of x-rays and IDDD revisions and or replacement).

7.12.1 Restrictions on the Number of Revision and/or re-implantation of the IDDD

A non-functional IDDD can be replaced or revised twice in a 6-month period, including the time a patient was in study HGT-SAN-055. Similarly, 6 X-rays may be taken in a 6-month period (including the time in HGT-SAN-055).

7.13 Cerebrospinal Fluid Opening Pressure Measurement

A CSF opening pressure measurement (cm of H₂O) will be conducted as per standard hospital practice. The measurement will be obtained whenever a LP is performed and an IDDD revision or replacement is done.

7.14 Dispensing Study Drug

rhHNS will be administered IT by means of an IDDD (or via LP if necessary) to patients on Day 2 (± 2 days) of Week 1 of each treatment month.

The patient may be sedated for this procedure. rhHNS will be administered through an appropriately sized syringe (see the Pharmacy Manual). If the IT space is not accessible via the IDDD, rhHNS may be administered via LP. See Section 6.2.4 for details.

7.15 Pharmacokinetic Assessments

Pharmacokinetic assessments are not included in this study.

7.16 Neurological Examination

A neurological examination to monitor CNS changes in a patient's neurological status will be conducted during this study. See [Appendix 2](#) for a complete list of the neurological examinations.

The neurological exam should not occur sooner than 4 hours after study drug administration or before the patient has fully recovered from any anesthesia administered for the dosing, whichever occurs later.

7.17 Anti-rhHNS Antibody, Heparan Sulfate, and Heparan Sulfate Derivative Determination

Blood samples will be collected and evaluated at Shire HGT laboratories for the determination of anti-rhHNS antibodies, and plasma and serum heparan sulfate and heparan sulfate derivatives. Samples will be reserved in accordance with local regulations for potential future MPS IIIA research that may determine biomarkers of disease severity and progression.

Two blood samples will be collected from each patient at each designated time point. One sample will be collected in tubes intended for serum specimens, while the second sample will be collected in tubes intended for plasma specimens. Blood sample collection, processing, and shipping instructions will be provided in the Laboratory and/or Study Operations Manual.

7.18 Neurocognitive and Developmental Assessments

Patients will undergo neurocognitive and neurobehavioral development testing. The assessments are estimated to last between 2 and 4 hours and must be conducted prior to sedation or anesthesia.

A full neurodevelopmental assessment, including global development, cognition, adaptive behavior, receptive and expressive language, and gross motor function, will be evaluated using standardized developmental and behavioral tests to provide a surrogate and quantifiable measure of global CNS neurodevelopmental/neurobehavioral function.

All patients will have received a series of standardized neurodevelopment assessments; in the HGT-SAN-055 study, patients in HGT-SAN-067 will continue with the age specific assessment they began with in HGT-SAN-055. If, however, a patient's capability improves and they become capable of completing assessments at a higher level, any such additional assessments may be added. Any additional assessments would be performed after the original assessments have been carried out.

For this study, outcome measures will be computed for each patient enrolled. The psychometric instruments and Sanfilippo-specific assessments are summarized below in [Table 7-1](#) and [Table 7-2](#), respectively. See [Appendix 2](#) for details on these assessments.

Table 7-1 Neurodevelopmental Assessments Tests

Developmental or Cognitive Domain(s)	Patient Age: Representative Cognitive Test or Scale
COGNITIVE DEVELOPMENT ASSESSMENT	
Summary score and sub-domains: - Cognitive - Motor - Social/emotional	0 to 42 months: Bayley Scales of Infant Development-III Bayley Scales of Infant Development, Third Edition (BSID-III) ²³
- Cognitive - Processing skills	3 to 18 years: Kaufman Assessment Battery for Children, Second Edition (KABC-II) ²⁴
GROSS AND FINE MOTOR SKILLS ASSESSMENT AND VOLUNTARY MOVEMENT	
Motor	3.0 to 16:11 years: Movement Assessment Battery for Children II (MABC-2) ²⁵
- Cognitive - Motor	0 to 5 ½ years: Bayley Scales of Infant Development III (BSID-III) ²³
ADAPTIVE BEHAVIOR	
Communication Daily Living Socialization Motor Skills	0 to 90 years: Vineland Adaptive Behavior Scales (VABS-II) Second Edition ²⁶

Table 7-2 Sanfilippo-Specific Disability Assessment And Behavior Rating Scales

DEVELOPMENTAL OR COGNITIVE DOMAIN(S)	SANFILIPPO SPECIFIC ASSESSMENTS
Parent-scored behavioral inventory - communication: understanding - communication: expression - tantrums - specific behaviors inventory - mood & emotions inventory	Sanfilippo Behavior Rating Scale (SBRS)
MPS-specific disability score - cognitive functioning - expressive language - motor score	Four-Point Scoring System/Total Disability Score (FPSS/TDS) ⁵

7.19 Sleep Questionnaire: Children’s Sleep Habits Rating Scale

A sleep questionnaire, Children’s Sleep Habits Rating Scale, will be administered to the patient's parent(s)/legally authorized representative(s).

7.20 Age-Dependent, Health-Related Quality of Life in Children

The Quality of Life questionnaires will be administered as outlined in Sections 7.20.1, 7.20.2, and 7.20.3.

7.20.1 Quality of Life Indicator: CHQ-50

The Child Health Questionnaire™ Parent Form 50 Questions (CHQ-50) will be administered during the study. The questionnaire is a generic quality of life instrument, measuring 14 unique physical and psychosocial concepts, which was developed for children from 5 to 18 years of age

7.20.2 Quality of Life Indicator: CHQ-87

The Child Health Questionnaire™ Child Form 87 (CHQ-87) will be administered during the study. The CHQ-87 is a child and adolescent self-report, developed for ages 10 and older, which assesses the child's self-perceived physical and psychosocial well-being

7.20.3 Quality of Life Indicator: ITQOL

The Infant Toddler Quality of Life Questionnaire™ (ITQOL) will be administered during the study. The ITQOL was developed for children at least 2 months of age up to 5 years and assesses the physical, mental, and social well being of the child and assesses the quality of the parent/legally authorized representative(s) life.

7.21 Concomitant Medications, Therapies and Medical/Surgical Procedures

All non-protocol treatments that occur from the time of informed consent (and assent, if applicable) through the safety follow-up contact are regarded as concomitant and will be documented on the appropriate pages of the eCRF. Concomitant therapy includes medication (including Genistein), therapies/interventions administered to patients, and medical/surgical procedures performed on the patients.

Every effort should be made to keep symptomatic Sanfilippo syndrome Type A treatment constant throughout the study. However, changes in medications are acceptable if necessary according to clinical judgment. All changes will be recorded on the appropriate eCRF. Concomitant medication will be coded using WHO-DD.

7.22 Adverse Events

7.22.1 Definitions of Adverse Events and Serious Adverse Events

7.22.1.1 Adverse Event

An adverse event (AE) is any noxious, pathologic, or unintended change in anatomical, physiologic, or metabolic function as indicated by physical signs, symptoms, or laboratory changes occurring in any phase of a clinical study, whether or not considered study drug-related. This includes an exacerbation of a pre-existing condition. Once the informed consent is signed and dated, any adverse event prior to the start of study drug must be reported.

AEs include:

- Worsening (change in nature, severity, or frequency) of conditions present at the onset of the study
- Intercurrent illnesses
- Drug interactions
- Events related to or possibly related to concomitant medications
- Abnormal laboratory values (this includes significant shifts from baseline within the range of normal that the Investigator considers to be clinically important)
- Clinically significant abnormalities in physical examination, vital signs, and weight

Throughout the study, the Investigator must record all AEs on the AE eCRF, regardless of the severity or relationship to study drug. The Investigator should treat patients with AEs appropriately and observe them at suitable intervals until the events stabilize or resolve. AEs may be discovered through observation or examination of the patient, questioning of the patient, complaint by the patient, or by abnormal clinical laboratory values.

In addition, AEs may also include laboratory values that become significantly out of range. In the event of an out-of-range value, the laboratory test should be repeated until it returns to normal or can be explained and the patient's safety is not at risk.

All adverse events should be recorded with causality assessment.

The information presented below is intended to provide issues to consider for AEs associated with intrathecal injections of rhHNS. In general, these AEs can be classified as follows:

- Adverse events due to systemic exposure to rhHNS caused by the drug diffusion from the CSF to the peripheral circulation;
- Adverse events related to the direct delivery of rhHNS to the intrathecal CSF space and meninges, and subsequent diffusion into brain parenchyma, via an intrathecal route
- IDDD-related AEs.

Note: the classification of potential AEs and the examples presented below are based on purely theoretical considerations and/or published literature as there is limited human experience with intrathecal rhHNS therapy to date.

POTENTIAL ADVERSE EVENTS: INTRATHECAL RECOMBINANT HUMAN HEPARAN N-SULFATASE

Adverse Events Due to Systemic Exposure to rhHNS

Although rhHNS is given intrathecally only, some proportion of the drug will diffuse from the CSF into the peripheral circulation. The resulting systemic exposure may cause events that are typically seen in patients receiving ERT via an intravenous administration, known as infusion-related reactions. An infusion-related reaction is defined as an adverse event that (1) begins either during or within 24 hours after the start of the infusion, and (2) is judged as possibly or probably related to study drug. Other AEs that occur prior to the infusion, along with AEs associated with protocol-defined testing and assessments (laboratory testing and physical examinations) that were performed prior to the infusion will not be defined as infusion-related reactions.

Adverse Events Related to the Direct Delivery of rhHNS to the CNS through Intrathecal Administration

Examples of adverse events observed in other published clinical trials with intrathecally-administered peptides or proteins, include, but are not limited to the following: headache, fever, feeling of warmth, sensory parathesias (including feelings of warmth, tingling, or pain) or autonomic symptoms such as dry mouth or gustatory abnormalities (including loss of smell and metallic taste). Changes in mental cognitive status or level of consciousness that are not caused by pre-medication may either occur acutely or develop post-injection, over time.

POTENTIAL ADVERSE EVENTS: IDDD-RELATED ADVERSE EVENTS

Examples of adverse events related to the insertion or use of an IDDD include, but are not limited to, the following: catheter disconnection or fracture, erosion of portal/catheter through the skin, fibrin sheath formation around the catheter tip, hematoma, implant rejection, malposition of catheter, migration of portal/catheter, occlusion of portal/catheter, portal site or subcutaneous tract infection, and sepsis.

In addition, there are risks associated with intraspinal access, which include the following: cerebrospinal fluid leaks, dura mater or epidural vein perforation, epidural or intrathecal space infection (which could result in meningitis), inadvertent epidural placement, pain on injection, and spinal cord or nerve injury.

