Probably Related	A clinical event or laboratory abnormality with a reasonable time sequence to administration of study drug, unlikely to be attributable to concurrent disease or other drugs and chemicals and which follows a clinically reasonable response on de-challenge. The association of the clinical event or laboratory abnormality must also have some biologic plausibility, at least on theoretical grounds.
Definitely Related	The event follows a reasonable temporal sequence from administration of the medication, follows a known or suspected response pattern to the medication, is confirmed by improvement upon stopping the medication (dechallenge) and reappears upon repeated exposure (rechallenge). Note that this is not to be construed as requiring re-exposure of the patient to study drug; however, the determination of definitely related can only be used when recurrence of event is observed.

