7.23 Safety-related Study Stopping Rules

If any patient experiences a life-threatening (Grade 4) adverse event or death which is considered possibly, probably, or definitely related to study drug, or if 2 or more patients experience a Grade 3 adverse event during the trial that is considered possibly, probably, or definitely related to the study drug by the sponsor, then the site will be instructed to halt further rhHNS administration to all patients and the safety data reviewed. Following a review of safety data, the study will be either:

- Resumed unchanged
- Resumed with modifications to the protocol or
- Terminated

Patient safety will be monitored on a continuous basis during this study until the last patient completes his or her last scheduled study visit/assessment.

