10.6 Efficacy, Safety, and Pharmacodynamic Evaluations

10.6.1 Primary Analyses

10.6.1.1 Safety Analysis

In general, safety assessments will be based on all assessments post-baseline. The assessment of safety will be based primarily on the frequency of adverse events, and on the frequency of clinically notable abnormal vital sign and laboratory values. Changes from baseline will be calculated by subtracting the baseline value from the post-baseline value.

All enrolled patients will be included in the safety analysis. Patients will be grouped according to the actual dose received.

No formal statistical test will be performed in the safety evaluations. Vital sign measurements, clinical chemistry, and hematology safety monitoring will be listed for each patient, and abnormal values will be flagged. These will also be summarized at each time point, including change from baseline.

Adverse events will be recorded throughout the study and at early termination. Adverse events and medical conditions will be coded using the Medical Dictionary for Regulatory Activities (MedDRA).

Adverse events will be summarized by presenting, for each treatment group, the number and percentage of patients having any adverse event, having an adverse event in system organ class, and having each individual adverse event. Note that in any given category (eg, system organ class) a patient will only be counted once. In addition, those events which resulted in death or were otherwise classified as serious will be presented in a separate listing. The incidence of treatment-emergent adverse events (new or worsened from baseline) will be summarized by system organ class, severity, type of adverse event and relationship to trial medication.

Adverse events that occur up to 30 days after the last dose of study drug will be considered “on-treatment”. Adverse events which are deemed probably, possibly, or definitely related to the device will be summarized by dose group and overall.

Laboratory data will be listed by patient and dose group. Patients with newly occurring abnormalities outside the normal range will be flagged and listed separately and summarized. Mean change from baseline values or shift tables will also be provided by dose group at each visit.

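### The infusion-related-reaction definition omits the strongest causality level, so a reaction judged definitely related is literally not classified as one

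*Protocol*

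**What the plan says.** Section 7.22.1.1, under adverse events due to systemic exposure, gives a numbered two-part definition of an infusion-related reaction. The event "begins either during or within 24 hours after the start of the infusion", and it "is judged as possibly or probably related to study drug". The section then names what is not to be called an infusion-related reaction: events before the infusion, and events tied to protocol testing done before it. It gives no other exclusion.

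Section 7.22.1.2 has the Investigator assign causality from Table 7-4, which has four levels: not, possibly, probably and definitely related. On the last, the table says that "the determination of definitely related can only be used when recurrence of event is observed".

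Elsewhere the protocol lists all three related levels. The stopping rule in Section 7.23 applies to events "considered possibly, probably, or definitely related to study drug". Section 10.6.1.1 states: "Adverse events which are deemed probably, possibly, or definitely related to the device will be summarized by dose group and overall".

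**The concern.** The definition stops one level short of the protocol's own scale, and the level left out is the one with the strongest causal evidence. The omission is not random with respect to the events it affects. Definitely Related is available only after observed recurrence, so every event that falls outside the definition for this reason has reappeared on re-exposure.

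The design gives room for this to happen. Dosing is every 28 days over a planned 4 years, and patients enter having received at least 5 of the 6 planned doses in HGT-SAN-055. A reaction that resolved and came back at a later dose is a candidate for the top level. If it is judged definitely related, it no longer meets the definition, although the same reaction judged only possibly related would.

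At stake is the meaning of the category. Anyone who later reports infusion-related reactions under this definition would report a set from which the best-documented cases are absent.

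**Working it through.** No figure in the protocol is in question, so there is no formula to reproduce. The check sets the related levels used in each place side by side.

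| Place in the protocol | Possibly | Probably | Definitely |
|---|---|---|---|
| Table 7-4 (the scale) | yes | yes | yes |
| Section 7.23, stopping rule | yes | yes | yes |
| Section 10.6.1.1, device-related summary | yes | yes | yes |
| Section 7.22.1.1, infusion-related reaction | yes | yes | **no** |

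The definition covers 2 of 3 related levels; the other uses cover 3 of 3.

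1. *Could the two-level wording be shorthand for at least possibly related?* Not safely. The levels are separately defined codes from which the Investigator chooses, and where the protocol means any related event it names all three.

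2. *Could the omission be deliberate?* The section states its exclusions, and Definitely Related is not among them. No reason for leaving it out is given.

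3. *Which events are affected?* Those with onset inside the 24-hour window that are judged definitely related. Recurrence is necessary for that level but not sufficient: Table 7-4 also asks for reasonable timing, a known or suspected response pattern and improvement when the drug is stopped. A recurrent reaction judged possibly or probably related still qualifies.

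4. *In which direction does the error run?* Let P be the number of in-window events judged possibly or probably related, and D the number judged definitely related. The definition yields P; a definition with all related levels yields P + D. The shortfall is D, which is never negative. The protocol gives no value for D, and it may be 0.

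5. *What happens per patient?* Section 10.6.1.1 says that "in any given category (eg, system organ class) a patient will only be counted once". A patient with even one in-window episode judged possibly or probably related still counts. A patient drops out of the category only if every in-window related episode was judged definitely related.

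**The case against.** The strongest reply is that nothing in the protocol depends on this definition. Section 10 names no infusion-related-reaction table, rate or endpoint. The passage is introduced as matters to consider and is said to rest on theory and published literature. A table of such reactions, if one is planned, would be in the SAP, which is not at hand. All of this is correct, and it limits the consequence. It does not mend the definition, which has the form of a rule, is the only one the protocol offers, and would be inherited by any later table.

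A reader might go further and infer that recurrent reactions vanish from the safety evaluation, biasing the primary safety question towards a favourable result. The documents do not support that. Section 7.22.1.1 requires all adverse events to be recorded whatever their relationship, with a causality assessment. Under Section 10.6.1.1 treatment-emergent events "will be summarized by system organ class, severity, type of adverse event and relationship to trial medication", serious events are listed separately, and all safety data are listed. The stopping rule includes the omitted level. No event leaves the data and no stopping decision changes.

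A reader might also put a large number on the loss: for example, a reaction recurring at ten doses, judged probably related once and definitely related thereafter, so that nine of ten episodes drop out, or all ten if the first episode was in HGT-SAN-055. Such figures assume the coding sequence and count episodes, whereas the stated rule counts patients once per category. In the first case the patient is still counted. In the second, baseline is the first dose in HGT-SAN-055 and safety uses all post-baseline assessments, so the earlier episode may itself fall within the analysis.

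**Conclusion.** The definition is wrong as written: it contradicts the protocol's own causality scale and leaves out reactions judged definitely related, a level open only to events that have recurred. The error runs one way, because any classification that follows the definition can understate infusion-related reactions and cannot overstate them. Its size is unknown and may be nil.

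This rests on a literal reading of criterion (2) and on Investigators using the top level of Table 7-4 at least sometimes. It is a misclassification within one category and not a loss of safety data, and it does not establish bias in the primary safety evaluation. Severity is minor to moderate.

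**What to change.** Extend criterion (2) in Section 7.22.1.1 to the same three levels that Section 7.23 uses, so that it covers events "considered possibly, probably, or definitely related to study drug". This adds one level to a list. Then re-derive the category for events already recorded.

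No new data are needed for causality, which is recorded for every event. On timing, Section 6.10 requires the date and time of dosing, while Section 7.22.2.2 names only the onset date of the event. If onset time is not on the case report form, the 24-hour criterion should be applied to the added events in the same way as to those already classified.

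The cost is a small text change and a minor programming change. No dose, visit or clinical rule is touched. The reported number of infusion-related reactions may rise.
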